5.4. Rationale for selection and measurement of endpoints

The endpoints are parameters describing the adherence of the ostomy tape to the skin and the potential effect on the skin. These are essential to investigate to understand, if the newly developed ostomy tapes have the ability to adhere to the skin without affecting it.

Adherent area: The adherent area after use shows how effectively the ostomy tape adheres to the skin. After removal of the ostomy tape, a photo of the tape is taken. The adherent area is measured from the photo and an image analysing program.

Erythema: A change in the surface skin colour is known to be related to a change in the blood flow. This can be measured non-invasively with a spectrophotometric instrument (Derma-spectrophotometer, Cortex Technology A/S, Hadsund) where both the redness and the colour of the skin are measured. Furthermore, visual assessments of photos have been used in several exploratory clinical investigations by Coloplast A/S to explore how adhesives affect the skin. The visual assessment is conducted by trained personnel and is a valuable tool for assessing newly developed adhesives and their impact on skin in the early development phases.

Feeling of security, adhesion of tape, comfort and skin issues: User experience is a very important part of product development in Coloplast A/S, and questions related to feeling of security, adhesion of tape and comfort relate to the user experience of how the ostomy tape adhere to skin while questions regarding skin issues relate to how the ostomy tape affects the skin.

Adverse Events: All Adverse Events are captured and documented throughout the study.

5.5. Demography and potential compromising factors

The following baseline information will be collected at V0:

- Gender
- Age
- Height/weight
- Reason for stoma
- Type of stoma
- Years with stoma
- Use of ostomy tape (Y/N)
- Use of other accessories (ring and paste)
- Usually stoma product used

To avoid treatments that may affect the skin, subjects may not be given chemotherapy or radiation treatment for two months prior to or while participating in the investigation. Subjects may not receive or have within the past month received systemic steroid or local treatment in the peristomal area and other areas of the skin tested.

The subjects can use ring or paste as they normal do during the study. But they are not allowed to use barrier creams or similar that affect the skin/adhesive interface under the tapes. Furthermore, the subjects may not use concave baseplate because the ostomy tapes are not designed for these baseplates.

5.6. Randomisation Procedure

All subjects that meet the inclusion and exclusion criteria will be randomised to one of six treatment arms. Each arm examines the comparator product and the 2 test products. The six possible arms are:

- Arm 1: Test product A, Test product B, and then comparator
- Arm 2: Test product B, Test product A, and then comparator
- Arm 3: Comparator, Test product A and then Test product B
- Arm 4: Comparator, Test product B and then Test product A
- Arm 5: Test product B, Comparator and then Test product A
- Arm 6: Test product B, Test product A and then Comparator

The randomisations list will consist of blocks of 6 and is centralised.

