10.1. Statistical design, method and analytical procedures

Definition of analysis populations

Intention to Treat (ITT) and Safety populations will be defined at a formal data review meeting just before database lock. As a minimum, the data manager, the clinical manager and the statistician will be involved in the classification of subjects.

The ITT population (full analysis set) will be constituted by all included subjects who:

- Have provided valid informed consent
- Have measurements for at least one of the endpoints or assessments

The Safety population will constitute by subjects who have given informed consent.

All statistical analysis and summaries will be based upon the ITT population whereas adverse events and Device deficiencies will be assessed based on the safety population. Invalid individual data points may be omitted from analysis even though the corresponding subject is part of the ITT population. Any exclusion of data points will be documented.

A formal PP population is not planned due to the explorative nature of the investigation.

Analysis of endpoints, individual questions and baseline data

All endpoints and individual questions as well as baseline/demographic data will be listed and summarized by descriptive statistics. The summaries for the endpoints and individual questions will be made for each product separately.

To explore potential indications of differences in adherent area the following analysis will be performed, if relevant. Adherent area can be analysed by a mixed repeated measures model using mean of the two adherent areas for each individual baseplate change as the observational unit. The model will consider that observations corresponding to different subjects are independent; whereas observations corresponding to the same subject are correlated. The correlation between observations corresponding to the same product can be larger than observations corresponding to different products. Hence the model includes a fixed effect of product (comparator product, test product A, test product B), a fixed period effect (period 1, 2, 3), a random effect of subject and a random interaction effect of product and subject. The model might be reduced by removing non-significant fixed effects, if relevant. All combinations of differences between the three products will be estimated.

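### Section 5.6 lists B, A, comparator twice (Arms 2 and 6) and omits A, comparator, B, so product is partly confounded with period

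*Combined protocol and SAP*

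**What the plan says.** Section 5.6 states that eligible subjects are "randomised to one of six treatment arms", with both test products and the comparator in every one, and a central list in blocks of 6. Writing C for the comparator, the first, third, fourth and fifth arms run ABC, CAB, CBA and BCA. The second is printed as "Arm 2: Test product B, Test product A, and then comparator", that is BAC. The sixth is the same sequence again: "Arm 6: Test product B, Test product A and then Comparator".

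Section 5.1 gives 12 subjects and three periods of 7 to 9 days.

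Section 10.1 describes an optional mixed model for adherent area with fixed product and period effects. It permits non-significant fixed effects to be taken out. A similar optional model is mentioned for erythema measured at the end of each period. For everything else the stated analysis is descriptive: "The summaries for the endpoints and individual questions will be made for each product separately". No period adjustment is described for those summaries.

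**The concern.** Three products have exactly six possible orders, and the plan has six arms and blocks of 6. The evident intention is to use every order once per block. The list as printed contains only five orders, one of them twice, and nothing in the plan says that doubling one order is intended.

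If the list was built from this text, product and period are no longer orthogonal. Two things follow:

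- The model-based comparisons lose some precision.
- Any analysis without a period term carries part of any period effect into the product differences.

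Period effects are plausible here. The study is open-label (Section 5.7). Subjects mark the lifted area and remove tapes themselves at home, a task they may get better at. The next product is applied at the visit where the previous one is removed, after half an hour of acclimatisation, with no washout (Section 7.2).

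**Working it through.** **Inputs.** The six sequences come from Section 5.6, with C for comparator: ABC, BAC, CAB, CBA, BCA, BAC. N = 12 comes from Section 5.1 and the block size of 6 from Section 5.6. Assumptions: each listed arm occurs once per block (so two subjects per arm) and all 12 subjects complete. The plan has no sample-size or precision calculation to reproduce (Sections 10.2 and 10.3).

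**Step 1: orders.** Of the 3! = 6 orders, BAC appears twice and ACB is missing.

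**Step 2: product by period (subjects).**

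| Product | Period 1 | Period 2 | Period 3 | Mean period |
|---|---|---|---|---|
| A | 2 | 6 | 4 | (2·1 + 6·2 + 4·3)/12 = 2.17 |
| B | 6 | 4 | 2 | (6·1 + 4·2 + 2·3)/12 = 1.67 |
| C | 4 | 2 | 6 | (4·1 + 2·2 + 6·3)/12 = 2.17 |
| All six orders, each product | 4 | 4 | 4 | 2.00 |

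First-order successions as listed are B→A 6, C→B 2 and the other four pairs 4 each. With all six orders every pair occurs 4 times.

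**Step 3: precision with period in the model.** Let σ² be the within-subject variance of a subject's mean for one product. Every subject receives every product, so the information matrix for products, adjusted for subject and period, is 12·I − (1/12)·n·nᵀ, where n is the count table above.

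- As listed: each diagonal element of n·nᵀ is 4 + 36 + 16 = 56. Each off-diagonal element is 44 (for A and B, 2·6 + 6·4 + 4·2). So n·nᵀ = 12·I + 44·J, where J is the matrix of ones. The information is 11·I − (11/3)·J = 11·(I − J/3), and every pairwise difference has variance 2σ²/11 = 0.1818σ².
- All six orders: n·nᵀ = 48·J, the information is 12·(I − J/3), and the variance is 2σ²/12 = 0.1667σ².
- Ratio: 12/11 = 1.091 for the variance and √1.091 = 1.044 for the standard error. Efficiency is 11/12 = 91.7%, so 12 subjects carry the information of 11.

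**Step 4: bias with no period term.** Let the period effects be p1, p2, p3. The bias in a difference of raw product means is the difference between two rows of the table, divided by 12:

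- A − C: (−2p1 + 4p2 − 2p3)/12
- B − C: (2p1 + 2p2 − 4p3)/12
- A − B: (−4p1 + 2p2 + 2p3)/12

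For a linear drift with effects 0, d, 2d:

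- A − C: (4d − 4d)/12 = 0
- B − C: (2d − 8d)/12 = −0.5d
- A − B: (2d + 4d)/12 = +0.5d

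A shift confined to period 2 biases A − C by 4/12, one third of the shift. With all six orders every coefficient is zero.

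**Step 5: sensitivity only.** The plan has no carryover term. If a first-order carryover term were added, the variances (in σ²) would be:

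| Contrast | As listed | All six orders | Increase |
|---|---|---|---|
| A − B | 0.2791 | 0.2083 | 34% |
| A − C | 0.2407 | 0.2083 | 16% |
| B − C | 0.2088 | 0.2083 | 0.2% |

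**The case against.** The best defence is that this is an exploratory pilot with no power calculation, no pass/fail criterion and a period effect already in the adherent-area model. With that term retained, period does not bias the product differences, and the loss is 4.4% on the standard error. That is correct, and the precision loss taken alone is modest.

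The line may also be a typing error. Arms 1 and 2 put the comparator last, Arms 3 and 4 put it first and Arm 5 puts it in the middle, so A, comparator, B would be the natural Arm 6. The actual list is not in the documents. If it holds all six orders, the design loses nothing and only the text is wrong. This also stands, and it is why the list should be checked first.

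The bias figures multiply a period effect whose size the plan does not give, so they cannot be turned into cm² or scale points. Calendar season would add little, since each subject takes part for at most 27 days. The carryover figures relate to a model that nobody has proposed, and 34% is the worst of three contrasts.

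The planned period term still does not settle the matter. The model is optional, and its period term may be removed when non-significant. With 12 subjects, non-significance is weak evidence that there is no period effect. In the balanced design, removing the term from complete data would leave the product estimates unchanged. In the listed design it would not. Security, adhesion, comfort, skin issues and photo-assessed erythema have no period-adjusted analysis described.

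**Conclusion.** The concern holds. Section 5.6 contradicts its own evident design: it names six arms but gives five orders, with B, A, comparator doubled and A, comparator, B missing.

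If followed as written, the cost is a 9.1% larger variance for every pairwise product difference when period is modelled. Where period is not modelled, linear drift leaks into B's comparisons at half the drift per period. B is the exposed product: 6 of 12 subjects use it first and only 2 use it last. All product differences remain estimable, so the confounding is partial.

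The counts rest on one use of each listed arm per block and on 12 completers. Withdrawn subjects are not replaced (Section 6.3), so the realised imbalance could differ.

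**What to change.** 1. Compare the actual randomisation list with Section 5.6. If it already holds all six orders, correct the text only.
2. Otherwise change Arm 6 to test product A, comparator, test product B. Regenerate the list in blocks of 6 and confirm that each product falls four times in each period across 12 subjects.
3. If subjects have already been allocated from the faulty list, their sequences cannot be repaired. State in Section 10.1 that period stays in every model whatever its p-value, and report period-adjusted product means in place of raw means. For items too sparse to model, tabulate by product and period.

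The cost is one corrected line and, where needed, a new list, with no extra subjects, visits or procedures. Section 12 requires a signed amendment with a change-log entry, and notification to the ethics committee (and the competent authority when appropriate) if the change counts as significant.

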5.7. Blinding

No blinding will be used in this investigation, as it is not possible to blind the products due to visible differences, except for the statistician who will be blinded until DBL.

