5.1. General

This investigation is a randomised, open-label, comparative, cross-over study, with three test periods.

In total, 12 subjects will be included and randomised, and each subject will have an inclusion visit and four test visits overseen by the Principal Investigator, or delegate. Each subject will be enrolled for three times 7-9 days in total for the entire investigation, thus for a maximum of 27 days – equal to at least 3 baseplates + tape change in each period. The subjects will test two new recipes of ostomy tapes and a comparator product in randomised order.

Between the test visits, the subjects will change products at home. At each product change, subjects will take a photo of the peristomal skin using a smartphone with a specially designed Clinical Trial app installed. Furthermore, they will answer questions about feeling of security, adhesion of tape, comfort and potential skin issues.

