5.3. Secondary endpoints

- Erythema measured after each treatment period by spectrophotometric method
- Erythema measured after tape removal by photos
- Feeling of security:
 - How was the feeling of security while wearing the tape?
(5-point scale from Very poor to Very good)
 - Did you feel confident that the tape would keep your base plate securely in place?
(5-point scale from Very little to Very much)
- Adhesion of tape:
 - How was the immediate adhesion to the skin?
(5-point scale from Very poor to Very good)
 - Did the edge of the tape lift/roll during use?
(5-point scale from Very poor to Very good)
- Comfort:
 - How comfortable was the tape to wear?
(5-point scale from Very uncomfortable to Very comfortable)
 - Did the tape allow you freedom of movement?
(5-point scale from Very little to Very much)
- Skin issues in the area covered by the tape:
 - Do you experience any **bleeding from the skin** under the tape right now when changing your product? (Experiencing/Not experiencing)
 - Once you have cleaned and dried the skin, do you experience any **weeping or moisture on the skin** under the tape right now when changing your product? (Experiencing/Not experiencing)
 - Are you experiencing any **ulcers or sores** under the tape right now when changing your product? (Experiencing/Not experiencing)
 - Did you experience complications where the tape was applied (like pain, stinging, itching, heat swelling or shiny skin)? (Yes/No)

- Please rate how painful the skin under the tape has been at its worst, since you last changed your product. (10-point scale from no pain (1) to worst pain possible (10))
- Please rate how itchy the skin under the tape has been at its worst, since you last changed your product. (10-point scale from no itch to worst itch possible)
- Adverse events

User experience with feeling of security, adhesion of tape, comfort and skin issues in the area covered by tape, will be assessed by prior mentioned questionnaires which will be assessed by interviews at Coloplast visit and self-reported by user at home.

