7.2. Visits

Baseline visit (V0):

- Introduction to the study
- Informed Consent and letter of authority signed
- Check of in- and exclusion criteria
- Visual evaluation of skin for inclusion
- Pregnancy test - dipstick (for women of child-bearing potential only)
- Inclusion in study and allocation of subject number
- Collect baseline information
- Possibility to accept interview by User Insight/development engineers/project members

Test visit 1:

- Randomisation
- Instruct subject in use of smartphone and Clinical Trial app and remind the subject to bring it for every study visit
- Remove tape/product with use of adhesive remover
- Photo of peristomal skin (digital camera)
- Acclimatization of peristomal skin for ½ hour
- Photo of peristomal skin after acclimatization (digital camera)
- Measurements of erythema
- Provide randomized test products or comparator products for the subject for change at home and apply 2 ostomy tapes on the peristomal skin (after ostomy product has been applied).
- Provide storage material for used ostomy tapes and adhesive remover
- Instruct and remind the subject to follow the study specific procedures between visits
- Schedule next visit in 7-9 days

Test visit 2 and 3:

- Follow up on subjects use of smartphone and Clinical Trial app and remind the subject to bring it for every study visit
- Ostomy tapes are removed with use of adhesive remover (before removing, mark the lifted tape area with a pen on the adhesive part)
- Photo of peristomal skin (digital camera)
- Photo of skin (smartphone – Clinical Trial App)
- Smartphone: Questionnaire about feeling of security, adhesion of tape, comfort & skin issues in the area covered by the tape
- Acclimatization of peristomal skin for ½ hour
- Photo of peristomal skin after acclimatization (digital camera)
- Measurements of erythema

- Provide randomized test products or comparator products for the subject for change at home and apply 2 ostomy tapes on the peristomal skin (after ostomy product has been applied).
- Provide storage material for used ostomy tapes and adhesive remover
- Instruct and remind the subject to follow the study specific procedures between visits
- Schedule next visit in 7-9 days
- Collect all used tapes and measure the adherent area
- Review AEs/ADEs/SAEs/SADEs
- Possibility to accept interview by User Insight/development engineers/project members

Termination visit 4:

- Follow up on subjects use of smartphone and Clinical Trial app

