7.3. Flow-chart

Table 3 chart showing the connection between visits and assessments.

	PERFORMED BY	BASELINE	TEST PERIOD	TEST PERIOD	TEST PERIOD	TERMINATION
VISIT WINDOW (DAYS)	-	-	-	7 - 9	7 - 9	7 - 9
GENERAL						
Subject information	Investigator	X				
Signed informed consent	Subject / Investigator	X				
Signed letter of authority	Subject / Investigator	X				

Allocation of subject number	Investigator	X				
Check of in- and exclusion criteria	Investigator	X				
Visual evaluation of skin for inclusion	Investigator	X				
Pregnancy test, dipstick (If applicable)	Investigator	X				
Randomization	Investigator		X			
Insurance of subjects' wellbeing and compliance with CIP	Investigator	X	X	X	X	X
COLLECTION AND REGISTRATION OF BASELINE DATA						
Demographics: Gender, age, height and weight	Investigator	X				
Stoma: Type, reason and duration	Investigator	X				
Use of ostomy tape (Y/N)	Investigator	X				
Use of other accessories (Ring and paste)	Investigator	X				
Usually stoma product used	Investigator	X				
Optionally interviews	Development engineers/project members			X	X	X
PROCEDURES						
Instruct in and follow up on subjects use of smartphone and Clinical Trial app	Investigator		X	X	X	X
Remind the subject to bring the smartphone at every study visit	Investigator		X	X	X	X
Mark the lifted tape area with a pen on the adhesive part, before removing the ostomy tapes	Investigator			X	X	X
Remove tape/product with use of adhesive remover.	Investigator		X	X	X	X
Photo of peristomal skin (digital camera)	Investigator		X	X	X	X
Photo of peristomal skin (smartphone)	Subject			X	X	X
Acclimatize peristomal skin for ½ hour	Subject		X	X	X	X
Smartphone, Questionnaire: Feeling of security, adhesion of tape and comfort	Subject			X	X	X
Smartphone, Questionnaire: Skin issues in the area covered by the tape	Subject			X	X	X
Photo of peristomal skin, after ½ hour acclimatization (digital camera)	Investigator		X	X	X	X
Measure erythema	Investigator		X	X	X	X
Provide test products to the subject	Investigator		X	X	X	
Apply ostomy product and ostomy test tapes (Test tapes should be applied at the edges of the baseplate)	Subject		X	X	X	
Provide storage material for used ostomy tapes and adhesive remover	Investigator		X	X	X	
Instruct and remind the subject to follow the study specific procedures between visits	Investigator		X	X	X	X

Schedule next visit	Investigator	X	X	X	X	
Collect all used tapes and measure the adherent area by photography	Investigator			X	X	X

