10.2. Sample size

Due to the conceptual nature of this trial (pilot evaluation of ostomy tapes under development) no formal sample size calculation has been performed. The evaluation will be supported by data from laboratory models. Twelve subjects are expected to provide enough information for further adjustment of the recipe.

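### Visible product differences do not justify unblinded reading of the erythema photos, which show skin after the tape is off; coded reading would be a cheap improvement

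*Combined protocol and SAP*

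**What the plan says.** Section 5.7 (Blinding) states: "No blinding will be used in this investigation, as it is not possible to blind the products due to visible differences". The one exception it makes is the statistician, until database lock.

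Section 5.3 lists as a secondary endpoint "Erythema measured after tape removal by photos". Section 5.4 says that trained personnel assess these photos visually, and calls the method "a valuable tool for assessing newly developed adhesives and their impact on skin in the early development phases".

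In section 7.2, at visits 2 to 4, the tape comes off first. A camera photo and a smartphone photo of the skin follow, and a second camera photo is taken after half an hour of acclimatisation. At home, too, tape removal precedes the photo. The flow-chart in 7.3 assigns the camera photos to the investigator and the smartphone photos to the subject. No section says which set is read for the endpoint. Section 11.1 describes central storage for the app photos only.

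On analysis, section 10.1 says: "The summaries for the endpoints and individual questions will be made for each product separately". No section mentions coding, random order or readers independent of the visits.

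**The concern.** The reason in 5.7 concerns the look of the product. It is then applied to everyone but the statistician, including people whose task is to look at skin from which the product has been removed.

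A reader who knows which tape was worn, and who expects a new recipe to be gentler or harsher, may score redness accordingly. That error goes straight into the per-product summaries. The effect on skin is the plan's only secondary objective (section 3), so a biased reading could colour what the sponsor learns about the recipes.

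**Working it through.** The plan has no figure to reproduce here. The check compares sections, followed by a count of photos.

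**1. Whom does the stated reason cover?**

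| Role | What is in view | Does the visible difference prevent blinding? |
|---|---|---|
| Subject | Applies and wears the tape (7.3) | Yes |
| Visit staff | Hand out and remove tapes (7.2, 7.3) | Yes |
| Reader of the used-tape photo (primary endpoint, 5.4) | The tape itself | Plausibly yes |
| Reader of the skin photo (5.3, 5.4) | Skin after tape removal (7.2) | Not for the reason given |
| Statistician | Finished readings | Already blinded (5.7) |

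**2. Do other design features remove the bias?** Let d be the shift a reader gives one product when it is recognised, and u the share of that product's photos that are recognised. The bias in the difference between that product and another is

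bias = u × d.

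Neither the number of subjects nor the number of periods appears in the expression. The cross-over removes differences between subjects, but d follows the product within each subject. The statistician receives readings already made. If every photo is recognised (u = 1), the bias is d. If coding leaves half or a quarter recognisable (assumed values), it is 0.5d or 0.25d. The documents give no value for d.

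**3. Do the other skin measures fill the gap?** In part.
- Spectrophotometry is listed after acclimatisation and only at visits (7.2, 7.3). Redness just after removal, and at home changes, is recorded only in photos.
- The questions in 5.3 cover bleeding, moisture, sores, pain, itch and similar complications, but do not name redness.
- Section 17.2 does not count temporary redness on removal as an adverse device effect.

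**4. Why hide period and visit date?** In section 5.6, arms 2 and 6 are the same sequence. With the six arms as written, the comparator is in period 3 in three of six (arms 1, 2, 6), product B is in period 1 in three of six (arms 2, 5, 6), and product A is in period 2 in three of six (arms 2, 3, 6). With balance each would be two of six. Knowing the period therefore raises a reader's best guess from 2/6 = 33% to 3/6 = 50%.

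**5. How many photos?** Inputs: 12 subjects, three periods, and for each period, from section 5.1, "equal to at least 3 baseplates + tape change in each period". The count assumes full attendance and treats the change at the visit as one of the period's changes.

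| Set | Sum | Photos |
|---|---|---|
| Camera, visits 2 to 4, only before acclimatisation | 12 × 3 × 1 | 36 |
| Camera, visits 2 to 4, before and after acclimatisation | 12 × 3 × 2 | 72 |
| App, 3 changes per period | 12 × 3 × 3 | 108 |
| App, 4 changes per period (assumed) | 12 × 3 × 4 | 144 |
| Both sets, 3 changes | 72 + 108 | 180 |
| Both sets, plus test visit 1 camera photos (12 × 2 = 24) | 180 + 24 | 204 |
| The same with 4 changes | 72 + 144 + 24 | 240 |

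Four changes is a reasonable upper case: with at least two days' wear, a nine-day period holds 9/2 = 4.5, so four whole wears.

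**The case against.** The strongest reply is that this is an optional refinement. The trial is an open-label pilot with no power calculation and no pass/fail criteria. Photo erythema is one of several secondary endpoints, no test is specified for it, and an instrument measures erythema as well. That stands, and it limits the weight of the point.

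The benefit also cannot be demonstrated from the documents. The readers are described only as trained personnel, and nothing says what they see with each photo. Taking u = 1 is therefore the worst case; 5.7 permits informed reading but does not show that every reading is informed.

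Third, the product descriptions are largely redacted. If the tapes differ in shape or size, an imprint on freshly uncovered skin could reveal the product, and the stated reason would then partly reach the photos. This is a fair limit on how complete masking can be. It is not a reason against coding, because partial masking still lowers u.

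Fourth, section 10.2 says "Twelve subjects are expected to provide enough information for further adjustment of the recipe", but it does not tie the photo reading to that decision and adds that laboratory data will support the evaluation. The photos are one input among several.

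Finally, which photos feed the endpoint is a matter of endpoint definition. It needs settling in its own right and adds no weight to the blinding argument.

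**Conclusion.** The concern holds. The reason in 5.7 does not extend to people reading photos of skin after tape removal, and nothing elsewhere masks that reading. This is a modest, worthwhile improvement; it does not invalidate the plan.

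The direction and size of any bias are unknown. Only its form is known: up to d in a product difference, and not reduced by recruiting more subjects. The conclusion assumes that readers can know or infer the product, which the plan allows, and that coding hides it in at least some photos. Calling the step cheap is a judgement from the count, about 36 to 240 photos depending on which are read; the documents give no cost.

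**What to change.** Replace the text of section 5.7 with wording such as:

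> Subjects and site staff who handle the tapes are not blinded, because the products are visibly different. The skin photos used for the visual erythema endpoint [state: camera, app or both; before acclimatisation, after it, or both] are coded without subject number, product, period or visit date. Trained personnel read them in random order; where possible, a reader did not handle that subject's visits. Data management holds the key until database lock. The statistician is blinded until database lock.

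State also where the camera photos are stored and, if readings are judged against test visit 1, put those 24 photos in the same coded set.

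The cost is one file-coding step. Subjects do nothing new, and neither the 12 subjects nor the two-sided 5% level changes. Coding can also be applied to photos already taken. If the trained personnel are the visit staff, they may need to exchange subjects, or masking will be weaker. Imprints, a visible baseplate or familiarity with the 12 subjects may leave some photos recognisable, and the report should say so. Section 12 gives changes to assessment methods as an example of a significant change, so the ethics committee and authority may have to be notified.
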